11.4.1.3. Exploratory Efficacy Analyses

Not applicable.

11.4.1.4. Clinical Benefit Analysis

The following clinical outcome analysis will be conducted:

- Net clinical outcome, defined as the composite of symptomatic recurrent VTE events, death as a result of VTE, and major and CRNM bleeding that occurred from the date of the first dose of study drug to the date of last dose of study drug + 30 days, will be analyzed using the same Cox proportional hazards regression model used for the primary efficacy analysis for mITT Analysis Set. The incidence of this endpoint will also be summarized by treatment for the mITT and PP Analysis Sets.

11.4.2. Pharmacokinetic/Pharmacodynamic Analyses

11.4.2.1. Pharmacokinetic Analyses

Plasma concentration and biomarker data will be summarized by age, dose, and time point using descriptive statistics for PK Analysis Set in this study.

The plasma concentration data will be pooled with data from other studies for a population PK analysis using nonlinear mixed effects modeling; the results will be provided in a separate report from the clinical study report for this study.

Exposure response relationships will be evaluated using Bayesian estimates of edoxaban exposure metrics (such as C_{av} , C_{max} , C_{trough} , and AUC) to explore relationships with safety and efficacy endpoints through a model based approach; the results will be provided in a separate report from the clinical study report for this study.

11.4.2.2. Pharmacodynamic Analyses

Pharmacodynamic data will be summarized by age, time point, and treatment arm using descriptive statistics for PD Analysis Set in this study.

11.4.2.3. Biomarker Analyses

Not applicable.

11.4.2.4. Pharmacogenomic Analyses

Not applicable

11.4.3. Safety Analyses

All safety analyses will be performed on the Safety Analysis Set, unless specified otherwise. Analyses will be based on the randomized treatment arm, unless a subject inadvertently receives

the incorrect drug during the entire study, in which case, the subject will be grouped according to the treatment actually received.

11.4.3.1. Analysis of bleeding events

An analysis will be performed for the composite safety endpoint of major and CRNM bleeding events which occur on-treatment from the first dose of study drug to 3 months + 3 days, or to the last dose of the study drug + 3 days if the subject permanently discontinued study drug prior to Month 3. The analysis of this endpoint is based on an “on treatment” approach. An event will be considered as an “on-treatment” event if it occurred while on study drug or within 3 days of randomized study drug interruption or discontinuation.

The time to “on-treatment” major and CRNM bleeding will be compared between treatment arms for subjects in the Safety Analysis Set, using the same Cox proportional hazards regression model as used for the primary efficacy analysis. Subjects who did not have an event will be censored at 3 days after the day of permanent study treatment discontinuation, or at 3 month + 3 days, or 6 to 12 weeks for Cohort 5, whichever occurred first.

Similar analyses will be conducted for all bleeding, as categorized below, occurred from the date of the first dose of study drug to the date of the last dose of study drug + 30 days using the Safety Analysis Set. Subjects who did not have corresponding event will be censored 30 days after the day of permanent study drug discontinuation.

Bleeding events will be summarized and analyzed for the following categories:

- Major and CRNM bleeding combined
- Any bleeding (major, CRNM, and nuisance, combined)

A sensitivity analysis will be conducted for major and CRNM bleeding, occurring while on-treatment, from the date of the first dose of study drug to the date of the last dose of study drug + 3 days during the whole study period. Subjects who did not have corresponding event will be censored 3 days after the day of permanent study drug discontinuation.

The incidence of bleeding events will also be summarized by treatment arm for on-treatment period up to 3 months + 3 days, on-treatment up to the date of last dose of study drug + 3 days, and from the date of the first dose of study drug to the date of the last dose of study drug + 30 days, using Safety Analysis Set.

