5.3. Dose Interruptions and Reductions

If a subject's treatment with study drug must be interrupted for medical or surgical reasons (eg, hospital admission for an invasive procedure, a major medical condition, surgery, thrombocytopenia due to cytotoxic medication, or dental work); use of a prohibited concomitant medication; or other reasons (eg, temporary situation that prevents subject adherence with the study drug administration schedule, etc.), the subject's study drug should be resumed as early as the situation allows. Edoxaban should be discontinued for 24 hours prior to the initiation of the procedures (depending on PK/PD data in children). Subjects should be encouraged to restart study drug after an interruption except when absolutely contraindicated. The duration of study drug interruption can vary depending upon the individual circumstances, and study drug may be resumed regardless of the duration of time that it had been interrupted. Any subject who temporarily interrupts study drug for more than 3 days will have the reason recorded in the electronic case report form (eCRF).

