11.4.1. Efficacy Analyses

11.4.1.1. Primary Efficacy Analyses

The primary efficacy analysis will be based on mITT Analysis Set. Analyses will be based on the randomized treatment arm even if a subject inadvertently receives the incorrect study drug. The primary efficacy endpoint is an event driven and a composite endpoint including symptomatic recurrent venous thromboembolic disease, death as result of VTE, and no change or extension of thrombotic burden from randomization to up to 3 months + 3 days from randomization. In this analysis, the time to the first event of the composite primary efficacy outcome will be analyzed using a Cox's proportional hazard regression model including treatment arm and age groups as covariates. Although this study is also stratified by region, region is not included in the model as a covariate because some age groups within regions may be very small due to the small overall sample size. The time to first event is defined as the time (days) from the day of randomization to the first event experienced by a subject during the 3 months + 3 days period. Subjects who did not have a primary efficacy outcome during the 3 months + 3 days period will be censored at 3 months + 3 days or the last day the subject had a complete assessment for study outcomes, whichever comes first. The edoxaban-to-comparator hazard ratio will be computed with 95% confidence interval (CI) (two-sided) based on this model. Edoxaban will be considered non-inferior to comparator if the upper limit of the 95% CI is ≤ 1.5 .

If non-inferiority of edoxaban is established, edoxaban will be tested for superiority to comparator. Edoxaban will be considered superior to comparator if the upper limit of the 95% CI from above analysis is ≤ 1.0 .

To control study-wise type I error, the testing for non-inferiority and superiority will follow the plan as described below.

The same proportional hazard model used for primary efficacy analysis will be performed for PP Analysis Set and Randomized Analysis Set as sensitivity analyses.

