11.4.1.2. Secondary Efficacy Analyses

The following secondary efficacy analyses will be conducted:

- A composite endpoint, including symptomatic recurrent venous thromboembolic disease, death as result of VTE, and no change or extension of thrombotic burden from the randomization to the date of the last dose of study drug + 30 days, the same Cox proportional hazards regression model used for the primary efficacy analysis will be used. The time to first event is defined as the time (days) from the day of randomization to the first event experienced by a subject from the randomization to the date of the last dose of study drug + 30 days. Subjects who did not have a primary efficacy outcome during the study period will be censored at the last day the subject had a complete assessment for study outcomes or the last study drug + 30 days, whichever came first. These efficacy analyses will be based on mITT and PP Analysis Sets. The incidence of this composite endpoint will also be summarized by treatment arm for the mITT and PP Analysis Sets.
- Incidence of all-cause mortality from randomization to the date of the last dose of study drug + 30 days will also be summarized by treatment arm for the mITT Analysis Set.
- The incidence of each component (symptomatic recurrent venous thromboembolic disease, death as result of VTE, and no change or extension of thrombotic burden) of the composite primary endpoint occurred during the first 3 month treatment period will be summarized by treatment arm for the mITT and PP Analysis Sets.

- The occurrence of DVT, catheter-related thrombosis, sinovenous thrombosis, and PE during the first 3-month treatment period, after the 3 month treatment period will be summarized by treatment arm for the mITT Analysis Set

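### The bleeding censoring rules keep subjects at risk when a bleed cannot count or cannot be seen, which biases the hazard ratio modestly if that time differs between arms

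*Combined protocol and SAP*

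**What the plan says.** Section 11.4.3.1 counts a bleed as on-treatment "if it occurred while on study drug or within 3 days of randomized study drug interruption or discontinuation". It then gives three censoring rules for subjects without an event:

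- **Main on-treatment analysis (major plus CRNM bleeding):** "censored at 3 days after the day of permanent study treatment discontinuation, or at 3 month + 3 days, or 6 to 12 weeks for Cohort" (the youngest age group), taking the earliest.
- **Whole-study on-treatment sensitivity analysis:** "Subjects who did not have corresponding event will be censored 3 days after the day of permanent study drug discontinuation".
- **Analyses to last dose + 30 days (major plus CRNM, and any bleeding):** "Subjects who did not have corresponding event will be censored 30 days after the day of permanent study drug discontinuation".

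The efficacy rules are built differently. Section 11.4.1.1 has event-free subjects "censored at 3 months + 3 days or the last day the subject had a complete assessment for study outcomes, whichever comes first". Section 11.4.1.2 uses "the last day the subject had a complete assessment for study outcomes or the last study drug + 30 days, whichever came first". The bleeding section borrows the efficacy Cox model but writes out its own censoring, so the last-assessment clause does not carry over.

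On interruptions, Section 5.3 says that "study drug may be resumed regardless of the duration of time that it had been interrupted", and that "Any subject who temporarily interrupts study drug for more than 3 days will have the reason recorded". On withdrawal, Section 5.6.4 reserves the term for subjects who can attend no further visit and lists death among the reasons. Section 6.5.2 notes that such subjects have no follow-up.

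**The concern.** In a Cox model a subject should be in the risk set only while an event could be both counted and observed. Two mismatches arise here, and they affect different analyses.

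(a) In the on-treatment analyses, a bleed from day 4 of an interruption onwards is excluded from the events, but the subject remains in the denominator until restart. That time is event-free by definition. The whole-study sensitivity analysis shares the flaw, so it cannot reveal it.

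(b) With no limit at last assessment or death, a subject who withdraws or dies is carried forward as bleed-free through days nobody observed.

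On-treatment major plus CRNM bleeding is the first secondary objective (Section 2.1.2) and the first safety endpoint (Section 9.2). The trial is open-label and compares an oral drug with injected or INR-titrated care, so unequal interruption or withdrawal is plausible, though the documents give no rates.

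**Working it through.** **1. The plan's own figure.** The documents give no bleeding rate, bleeding margin or bleeding sample size. The only sizing figure is the 68 efficacy events in Section 11.6. Schoenfeld's formula gives 4 × (1.960 + 0.842)² / [ln(1.5/0.76)]² = 67.9, so 68 reproduces. This point does not affect it.

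**2. The rules side by side.**

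| Analysis | Bleed on day 4+ of an interruption counts? | Subject at risk then? | Limit at last assessment or death? |
|---|---|---|---|
| On-treatment, to 3 months + 3 days | No | Yes | No |
| On-treatment, whole study + 3 days | No | Yes | No |
| To last dose + 30 days | Yes | Yes | No |
| Efficacy, primary and secondary | Not applicable | Not applicable | Last assessment: yes |

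Mismatch (a) is confined to the first two rows. Mismatch (b) touches all three bleeding rows, but for very different lengths of time.

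**3. Formula.** Let f be the share of an arm's risk time in which no event can count or be seen. With a true HR of 1.0 and a roughly constant hazard, the apparent HR (edoxaban to SOC) is (1 − fE)/(1 − fC). Equal shares give 1.00.

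**4. Assumed scenarios.** Each was also checked by a large Cox simulation with an assumed 10% bleeding risk over 93 days (simulation error about 0.01). Imbalances are written edoxaban versus SOC.

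- *14-day interruptions in 40% vs 10%.* Uncountable days per interruption: 14 − 3 = 11. fE = 0.40 × 11/93 = 4.7%; fC = 0.10 × 11/93 = 1.2%. HR = 0.953/0.988 = 0.96. Simulation: 0.97 (reversed, 1.04).
- *28-day interruptions in 30% vs 10%.* Uncountable days: 28 − 3 = 25. fE = 0.30 × 25/93 = 8.1%; fC = 0.10 × 25/93 = 2.7%. HR = 0.919/0.973 = 0.94. Simulation: 0.94 (reversed, 1.06).
- *Withdrawals of 20% vs 5%, last dose + 30 days.* Assume last dose equals last contact, spread evenly over days 1 to 90 (mean 45.5), and that other subjects contribute 120 days. A withdrawn subject is credited with 75.5 days, 30 of them unobserved. fE = (0.20 × 30)/(0.80 × 120 + 0.20 × 75.5) = 6/111.1 = 5.4%; fC = (0.05 × 30)/(0.95 × 120 + 0.05 × 75.5) = 1.5/117.8 = 1.3%. HR = 0.946/0.987 = 0.96. Simulation: 0.96 (reversed, 1.04).
- *The same withdrawals, main on-treatment analysis.* Only 3 unobserved days are added per withdrawn subject. fE = 0.6/84.1 = 0.7%; fC = 0.15/90.8 = 0.2%. HR = 0.99, and the simulation agrees. If no discontinuation date is recorded and the subject runs on to 3 months + 3 days, the simulation gives 0.92 (reversed, about 1.08).

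Taking the uncountable or unobserved time out of the risk set returned 1.00 within simulation error.

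**5. Precision.** An assumed bleeding risk of 5% to 15% in 274 subjects gives 274 × 0.05 = 13.7 to 274 × 0.15 = 41.1 events. The 95% limits are the HR multiplied and divided by exp(1.96 × 2/√events), that is 2.9 down to 1.8.

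**The case against.** The strongest reply is that the effect is small and no decision rests on it. Bleeding has no margin and was not sized, and the shift is far inside the confidence interval. That stands, and it limits the weight of the point.

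Second, few subjects are truly unobserved. Sections 5.6 and 5.6.1 keep subjects who stop treatment early under follow-up to Month 3 and a 30-day visit, with telephone contact allowed. That also stands: mismatch (b) concerns only genuine withdrawals and deaths.

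Third, Section 11.7 leaves definitions and missing-data handling to a SAP whose separate text was not available for this review. This stands only in part. Section 11.4.3.1 already states explicit censoring rules, and a programmer who follows them will produce the mismatch. Interrupted time is also a matter of risk-set definition, not of missing data.

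A reader might infer more than the documents support:

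- *That both mismatches distort the main safety comparison.* Interruptions do. The last-contact gap adds only about 3 days per withdrawn subject there, if a discontinuation date is recorded.
- *That the HR could fall to 0.90 or 0.84.* Those values need arm-wide shares such as 10% vs 0% or 20% vs 5%. On 93 days, 20% is 18.6 days per subject. With 14-day interruptions that takes 18.6/11 = 1.69 interruptions for every subject in the arm; with 28-day interruptions, 18.6/25 = 74% of the arm. Nothing in the documents points to that.
- *That the less tolerated arm, or edoxaban, is necessarily favoured.* Section 9.2.1 makes an overt bleed that leads to interruption a CRNM event at least, so in a first-event analysis that subject has already left the risk set. The 24-hour edoxaban stop before procedures in Section 5.3 falls within the 3-day allowance by itself. The imbalance could run either way.

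**Conclusion.** The point holds as a mismatch between stated event and censoring rules. Time from day 4 of an interruption is wrongly kept at risk in the two on-treatment analyses, and every bleeding rule lacks a death or last-assessment limit, which matters mainly in the analyses to last dose + 30 days.

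The HR is affected only if interruptions or withdrawals differ by arm. In the scenarios tried, the shift is about 3% to 6% either way. These figures rest on assumed interruption and withdrawal frequencies, a constant hazard and a true HR of 1.0, because the documents supply no rates. The 0.92 case further requires missing discontinuation dates. Equal shares leave the HR unbiased, though absolute bleeding rates per unit of time would still be understated.

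The rules should be corrected before database lock because correction is cheap. The point does not threaten the trial's conclusions.

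**What to change.** 1. Add to every bleeding censoring rule in Section 11.4.3.1: or death, or the last date on which bleeding status was assessed, whichever is first.
2. In both on-treatment Cox analyses, use start-stop (counting-process) intervals that take a subject out of the risk set from day 4 of an interruption until restart.
3. Name the planned analysis of major plus CRNM bleeding to last dose + 30 days as the supportive check. As written it has no interruption exclusion, so it counts bleeds during interruptions and no new analysis is needed.

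**Cost.** SAP wording and minor programming; no extra visits, subjects or endpoints. Interruption and restart dates are needed in both arms. Section 5.3 mentions only the reason for interruptions over 3 days, and Section 5.4 tracks SOC compliance by laboratory levels, so the eCRF should be checked for dates. They are already required to apply the plan's own 3-day event rule. Removing interrupted time also assumes that interruption is uninformative about bleeding, which the SAP should state.

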5.1.1.2. Standard of Care Treatment Arm

SOC treatment will be dispensed to the subject on a monthly visit schedule. After Month 3, the distribution of SOC may be for a 3-month period to align with the visit schedule, with the Sponsor's approval. Subjects will receive SOC anticoagulant according to the site's SOC treatment, as follows (alone or combination):

- LMWH (alone or followed with VKA)
- SP Xa inhibitors (alone or followed with VKA)
- Vitamin K antagonist (VKA)

In case of centrally sourced SOC treatment, the Sponsor will only provide enoxaparin as LMWH, fondaparinux as SP Xa inhibitor, or warfarin as VKA with limited presentations. The subject will be treated with enoxaparin or fondaparinux or warfarin/heparin, with the following suggestion:

- Enoxaparin – Subjects will be treated with enoxaparin alone or can be switched to warfarin anytime during the study treatment period. Single dose (pre-filled syringe) or as multiple dose vials (for subjects <10 kg) for injection where allowed per standard clinical practice will be provided to the subject. Initial treatment age-dependent dose of enoxaparin:
 - Age <2 months: 1.5 mg/kg dose twice a day
 - Age ≥ 2 months: 1.0 mg/kg dose twice a day
- Fondaparinux – Subjects will be treated with fondaparinux alone or can be switched to warfarin anytime during the study treatment period.
 - Dosing of 0.1 mg/kg/day (0.05 mg/kg/day for subjects with renal disease).
 - If the appropriate required dose cannot be administered with the pre-filled syringes, the site should consider using alternative SOC treatment options.
- Warfarin will be started on Day 1. Heparin will be discontinued when INR ≥ 2.0 and ≤ 3.0 for 2 consecutive measurements obtained at least 24 to 48 hours apart. The subject will continue warfarin treatment for the remainder of the study treatment period.
 - Additional information on dosing and dose adjustment (Appendix 17.2)

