5.5. Prior and Concomitant Medications

Medications that the subject has taken within 30 days before randomization will be recorded.

There are no concomitant medications required as part of the study design. The following drugs and devices (see [Appendix 17.4](#)) CANNOT be used during the entire study treatment period and their unavoidable use would require study drug therapy interruption unless specifically indicated for study drug discontinuation:

- Anticoagulants, other than the assigned study drugs, by any route – study drug discontinuation
- Fibrinolytic agents, if required to treat thromboembolism events, require study drug discontinuation and consideration of a transfusion of fresh frozen plasma;
- Single or dual antiplatelet therapy with any antiplatelet agent is prohibited except for low dose aspirin defined as 1-5 mg/kg/day with maximum of 100 mg/day. If a

clinical indication for antiplatelet therapy (other than low dose aspirin) arises after randomization, study drug should be discontinued.

- Chronic use of oral or parenteral NSAIDs including both cyclooxygenase-1 (COX-1) and cyclooxygenase-2 (COX-2) inhibitors other than aspirin for ≥ 4 days/week. Use of NSAIDs via other routes (eg, topical, inhaled, intranasal, intraocular, etc.) are not restricted (see Appendix 17.4.5).

All P-gp inhibitors (please refer to Appendix 17.4.6 for an example list of most commonly used P-gp inhibitors) excluding amiodarone will require dose reduction of edoxaban.

The Investigator is encouraged to contact a study physician (telephone number will be provided per country, per region; please refer to Study Manual for an appropriate phone number) if further guidance is needed.

Information regarding concomitant medications will be collected with start date, stop date, drug name, dose and dosing regimen for population PK analyses.

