- For subjects in whom clinicians prescribe warfarin, this will be started on Day 1. Heparin (exoxaparin or fondaparinux or UFH depending on the therapy received during pre-randomization period) will be discontinued when INR ≥ 2.0 and ≤ 3.0 for 2 consecutive measurements obtained at least 24 to 48 hours apart. The subject will continue warfarin for the remainder of the study treatment period.

The Investigator will use discretion to decide when and how often to repeat INR or anti-FXa levels or aPTT measurements or fondaparinux levels. These measurements will be taken in the clinic, or alternatively, optional site-specific local laboratory (Appendix 17.2).

6.3.3. Monthly Visits (Months 1 and 2; Visits 3 and 4) for both arms:

Starting with the Month 1 visit, subjects will return to the clinic every 30 days \pm 5 days (depending on the visit, see Schedule of Events in Appendix 17.1) until the Month 3 visit (Visit 5) or study withdrawal. For Cohort 5, the subjects may return to the clinic earlier after the first month, depending on the duration of the therapy (at least 6 to 12 weeks) and imaging at 6 weeks for thrombus resolution.

During study drug interruptions and after study drug discontinuation, subjects will be followed for efficacy and safety endpoints and SAEs until the Month 3 visit (Visit 5) or earlier in Cohort 5 subjects (6-12 weeks). A 30 day Follow-Up Visit (Visit 9) for safety assessment is required after the Month 3 visit (for Cohort 5, the intended duration of treatment is 6 to 12 weeks).

At these monthly on-site visits, anti-FXa levels assessments and aPTT measurements will be performed for the subjects on SOC with LMWH or SP Xa inhibitor, fondaparinux levels if applicable, and INR assessments will be performed for the subject on SOC with VKA. Additional interim visits may be scheduled, at the Investigator's discretion, for anti-FXa levels/INR monitoring.

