17.4. Prohibited Concomitant Medications

The list here (in the protocol) is static and reflects the list at the time of the current version of the protocol. If there are changes to this list during the study, the changes will not be considered a protocol amendment and the list in this appendix will not be updated unless the protocol is being amended for other reasons as well.

Subjects on these drugs at the time of planned randomization will be excluded from the study. After randomization, use of these drugs will require a study drug permanent discontinuation unless advised otherwise in the sections below. The Investigator is encouraged to contact the Medical Monitor for further guidance.

Sites will receive a contact card where the following numbers (24-hour Urgent Medical Contact) are provided:

PPD [REDACTED] (primary number)
PPD [REDACTED] (alternative number)

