17.4.3. Parenteral Anticoagulants

Parenteral anticoagulants are prohibited in the edoxaban treatment arm. Direct thrombin inhibitors are prohibited in edoxaban arm and in the SOC arm.

Examples of prohibited parenteral anticoagulant medications include the following:

- Low molecular weight heparins: enoxaparin (Lovenox®, Clexane®), dalteparin (Fragmin®), tinzaparin (Innohep®, Logiparin®), reviparin (Clivarin®), nadroparin (Fraxiparine®), ardeparin (Normiflo®), certoparin (Sandoparin®), parnaparin (Fluxum®)
- Direct thrombin inhibitors: bivalirudin (Angiomax®), argatroban, (Acova®), desirudin (Iprivask®), lepirudin (Refludan®)
- FXa inhibitors: fondaparinux (Arixtra®)

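### The on-treatment bleeding analysis censors at a discontinuation that means different things in the two arms; add one sensitivity analysis to 3 months + 3 days regardless of discontinuation

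*Combined protocol and SAP*

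**What the plan says.** **Censoring and event window (Section 11.4.3.1).** For the composite of major and CRNM bleeding: "Subjects who did not have an event will be censored at 3 days after the day of permanent study treatment discontinuation", or at 3 months + 3 days (6 to 12 weeks in Cohort 5), whichever comes first. A bleed counts "if it occurred while on study drug or within 3 days of randomized study drug interruption or discontinuation". A second set of analyses runs from first dose to last dose + 30 days. The one stated sensitivity analysis uses last dose + 3 days over the whole study.

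**SOC arm (Section 5.1.1.2).** Treatment is LMWH, a synthetic pentasaccharide or a VKA, alone or combined. For centrally supplied drug: "Subjects will be treated with enoxaparin alone or can be switched to warfarin anytime during the study treatment period". Fondaparinux has the same permission. Such a child has not discontinued.

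**Edoxaban arm.** Appendix 17.4.3: "Parenteral anticoagulants are prohibited in the edoxaban treatment arm". Section 5.5 attaches study drug discontinuation to "Anticoagulants, other than the assigned study drugs, by any route". Appendix 17.4 adds: "After randomization, use of these drugs will require a study drug permanent discontinuation unless advised otherwise in the sections below".

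**Follow-up.** Section 6.3.3: "after study drug discontinuation, subjects will be followed for efficacy and safety endpoints and SAEs until the Month 3 visit", with an earlier end in Cohort 5. Section 15.10 sends suspected endpoint events to blinded adjudication even when the subject has permanently stopped study drug.

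**The concern.** SOC is a strategy with several drugs and edoxaban is one drug, so a single censoring rule gives different at-risk time by arm. Take two children whose anticoagulant is changed on day 30, one from enoxaparin to warfarin in SOC and one from edoxaban to LMWH. Each has a major bleed on day 70. The SOC bleed is in every analysis. The edoxaban child left the on-treatment analysis on day 33 and the last dose + 30 days analysis on day 60, so that bleed is in none of them, although it was followed up and adjudicated.

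This matters if a change of drug marks a child with a different bleeding risk. The documents make that plausible without quantifying it: Section 1.1 notes that severe underlying disease often rules out early oral treatment, so that LMWH is continued. Such a child can stay at risk in SOC but may leave the edoxaban risk set.

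At stake is the main safety comparison, which Section 9.2 calls primary for Cohort 5. The primary efficacy analysis does not share the problem: Section 11.4.1.1 censors at 3 months + 3 days or the last complete assessment, not at discontinuation. Bleeding has no counterpart to that analysis.

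**Working it through.** **The plan's own figure.** None is given for bleeding. The efficacy figure reproduces: 4 × (1.960 + 0.842)² / [ln(1.5/0.76)]² = 31.4 / 0.462 = 67.9, so 68 events. The expected number of subjects is 68 / [(0.28 + 0.2128)/2] = 276, against 274 stated.

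**Inputs for the illustration.** From the documents: a 93-day window (3 months + 3 days) and censoring at change + 3 or + 30 days. Assumed, because the documents give no bleeding or switching rates: true hazard ratio 1; 15% bleeding risk over 93 days in ordinary subjects; a share f of 10% or 15% who change drug on day 21 or 30; these bleed at k times the ordinary rate throughout. All edoxaban changers are censored and all SOC changers are kept, which is the extreme case. The + 30 days analysis is cut at day 93 for simplicity.

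**One case by hand: f = 15%, k = 3, change on day 21, censored on day 24.**
- Ordinary daily hazard: −ln(0.85)/93 = 0.001748. Changers: 3 × 0.0017475 = 0.005243.
- Ordinary subjects, either arm: 0.85 × 0.15 = 0.1275 bleeds; 0.1275/0.001748 = 72.96 days (both per subject randomized).
- SOC changers: 0.15 × (1 − 0.85³) = 0.0579 bleeds; 0.0579/0.005243 = 11.04 days.
- Edoxaban changers: 0.15 × (1 − exp(−0.005243 × 24)) = 0.0177 bleeds; 3.38 days.
- SOC rate: 0.1854/84.00 = 0.002207. Edoxaban rate: 0.1452/76.34 = 0.001902. Rate ratio 0.862; incidence ratio 0.1452/0.1854 = 0.783.
- With + 30 days (day 51), edoxaban changers contribute 0.0352 bleeds and 6.71 days: 0.1627/79.67 = 0.002042, rate ratio 0.925.

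**Cox version.** The large-sample hazard ratio θ solves Σ [D_E(t) − D(t) · θR_E(t) / (θR_E(t) + R_S(t))] = 0, where D is bleeds (D_E those on edoxaban) and R_E, R_S are the shares still at risk on edoxaban and SOC.

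| f | k | Day of change | HR, + 3 days | HR, + 30 days | Incidence ratio, + 3 days |
|---|---|---|---|---|---|
| 10% | 2 | 30 | 0.949 | 0.974 | 0.896 |
| 10% | 3 | 21 | 0.899 | 0.943 | 0.846 |
| 15% | 2 | 21 | 0.915 | 0.952 | 0.825 |
| 15% | 3 | 21 | 0.859 | 0.922 | 0.783 |
| 15% | 1 | 21 | 1.000 | 1.000 | 0.891 |
| 15% | 0.5 | 21 | 1.060 | 1.035 | 0.938 |

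The crude on-treatment incidence, which Section 11.4.3.1 also tabulates, falls even at equal risk because exposure is shorter.

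**If SOC also loses subjects.** Take 20% of subjects at 3 times the rate, half of them leaving the edoxaban arm over the window, and 5% overall bleeding risk. The hazard ratio is 0.94 if SOC loses none, 0.97 if SOC loses them half as often, and 1.00 if equally often.

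**Random error.** With 274 subjects, a 15% risk gives 41 bleeds: the standard error of the log hazard ratio is 2/√41.1 = 0.312, so the 95% limits lie a factor exp(1.96 × 0.312) = 1.84 either side. A 5% risk gives 13.7 bleeds and a factor of 2.88.

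**Interruption or discontinuation.** Sections 5.3 and 5.6.6.1 list use of a prohibited medication among reasons for temporary interruption, with study drug resumed. Section 5.5 and Appendix 17.4 say discontinuation. On the interruption reading the child is not censored, but bleeds more than 3 days into the gap do not count. If 15% of edoxaban subjects only had 14 uncounted days, the ratio at equal risk would be about 1 − 0.15 × 14/93 = 0.98.

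**The case against.** On-treatment bleeding is a legitimate safety question, and much of the case against this point stands.

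- A reader might infer that fragile children leave the edoxaban arm only. The documents do not support that. The reasons for stopping in Section 5.6.3 apply to both arms, and direct oral anticoagulants and direct thrombin inhibitors are prohibited in both (Appendices 17.4.2 and 17.4.3). SOC children who stop or take such an agent are censored by the same rule.
- A reader might also infer that edoxaban will simply look safer. That needs changers to bleed more *later*. A bleed that itself prompts a change of therapy is already a CRNM event (Section 9.2.1), so it is not lost.
- The SOC change spelled out is enoxaparin or fondaparinux to warfarin, a planned sequence that nothing ties to illness. Whether a warfarin child may return to a parenteral agent is not spelled out.
- Procedures, surgery and major illness are handled as interruptions in Section 5.3, and so need not end follow-up.
- The last dose + 30 days analysis roughly halves the bias in the table.
- Random error is larger than any shift shown.
- Sections 11.4.3.6 and 11.7 leave further analyses and missing-data handling to the SAP, so the gap is shown only for the text of Section 11.

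What survives is the arm-dependent meaning of discontinuation, and the fact that every analysis in Section 11.4.3.1 is tied to the last dose.

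**Conclusion.** The point holds as differential, possibly informative censoring that could favour edoxaban; it is not a demonstrated bias. Over the assumed range, a true hazard ratio of 1.0 appears as about 0.86 to 0.95 in the main analysis and 0.92 to 0.97 in the last dose + 30 days analysis. The effect vanishes from the hazard ratio at equal risk, turns to about 1.06 if changers bleed at half the ordinary rate, and shrinks as SOC censoring approaches that on edoxaban. Bleeding risk, share changing, timing and relative risk are all assumptions. The shift is modest beside the sampling error, but the data to examine it will already be in hand. This is a worthwhile, inexpensive addition and does not invalidate the planned analysis.

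**What to change.** Add one pre-specified sensitivity analysis to Section 11.4.3.1: adjudicated major plus CRNM bleeding from first dose to 3 months + 3 days (Cohort 5: its own window), regardless of discontinuation or change of anticoagulant. Use the Safety Analysis Set and the same Cox model, and censor at last contact. Tabulate discontinuations and changes of anticoagulant by arm, time and reason.

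Reconcile Sections 5.3 and 5.6.6.1 with Section 5.5 and Appendix 17.4 on whether use of a prohibited anticoagulant is an interruption or a discontinuation, because that decides who is censored.

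Do not try to restore symmetry by censoring SOC children at their first change of drug class. That would remove those following the planned sequence from LMWH or fondaparinux to a VKA, and with them their VKA exposure.

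The cost is one extra model and one table on data already collected. The downside is that counting bleeds after a change of drug dilutes drug-specific effects, so the new analysis supports the on-treatment analysis and does not replace it.
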